7.6 Time-Dose Considerations

- ◊ Dose per Fraction: 3.33 Gy to the prescription point
- ◊ Deliver one fraction per day.
- ◊ Total Elapsed Time is 15-19 days.

NOTE: Patients may have missed treatment days due to acts of nature or personal/medical emergencies. Typically 1-2 missed days are simply added to the end of the treatment course for the same total dose. Greater than 2 skipped days or greater than 3 consecutive days without treatment (one missed day plus weekend) will be discussed by study investigators and decision to retain patient on treatment or remove patient from study will be made by consensus decision of [REDACTED]

[REDACTED]

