4.2.1 Study Schema – Postmastectomy radiation therapy

If chemotherapy is indicated and is delivered after RT, it must start ≥ 21 days after completion of RT.

RT time = 11 weekdays (once/day) chest wall irradiation = 11 RT days

Total Elapsed Time = 11 total weekday RT = 15 elapsed days (mastectomy scar boost optional up to 4 fractions)

5. Study Enrollment Criteria

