5.6 Study Enrollment Procedures

Accelerated, Hypofractionated Chest Wall Radiotherapy in Women with Breast Cancer: A Phase II Trial
 [REDACTED]

6. Study Parameters

Evaluations	Prior to treatment	During Radiation (weekly)	FOLLOW-UP (after radiation therapy)		
			End of Radiation and 2-8 weeks after RT	Then every 3-9 months (for 3 yrs)	Then every 6-15 months (out to 5 yrs)
Signed informed consent	X				
History & Physical	X	X	X	X	X
Pregnancy test (B-HCG)	X ¹				
Chest wall CT (Simulation)	X ²				
Optional serum and tumor tissue samples	X ³				

1. Within 7 days before starting treatment if of child bearing age. For menopausal status, see Appendix C.

2. After surgery/chemotherapy for treatment planning

3. For optional correlative studies, patients will be offered co-enrollment in CINJ Study # 040703 (IRB 0220070169). See Sections 9.4 and 11.

4. End of radiation = During the last 3 fractions of radiation

7. Treatment Plan

Postmastectomy RT consists of 3663 cGy in 11 fractions (333 cGy) over 11 weekdays (for 15 elapsed days); no boost is required, optional chest wall boost upto 4 fractions of 3.33 cGy is allowed (total 1332 cGy).

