7.5 Treatment Dose

Postmastectomy chest wall will get 3663 cGy in 11 fractions; a scar boost is optional at the discretion of the treating physician, upto 1332 cGy in 4 fractions. Treatment may be started on any weekday, and will not be given over holidays or weekends.

- ◊ **Prescription Point**

7.5.1 Dose from the chest wall fields can be prescribed at a point 1.5 cm anterior to the posterior edge of the fields at mid-separation, or to a point 1/3rd the distance from this point to the skin, or to an isodose line encompassing the PTV. IMRT technique and other highly conformal techniques are allowed.

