7.9 Quality Assurance of Dose Distribution

Each treatment plan shall be judged as:

- **Acceptable:**
 - Dose volume histogram analysis of the target volume confirms 90% of the prescribed dose covers $\geq 90\%$ of the PTV.
 - Dose delivered once a day for 11 daily treatments for PMRT on consecutive weekdays.
 - No greater than 3 cm of lung should be visible at any level of the tangent beam on beam's eye view.

- Heart excluded from primary beam on chest wall fields. If the heart is included in the field, no greater than 1cc of a heart is allowed to receive a fraction dose exceeding 2 Gy.
- Minimum and maximum doses within 90-115% of prescription dose.
- Electron plans (typically for the scar boost) allow 120% of prescription dose as maximum dose provided the volume receiving 120% does not exceed 2 cc.
- **Unacceptable:**
 - Dose volume histogram analysis of the target volume shows < 90% of the prescribed dose covers < 100% of the PTV.
 - Maximum dose on the whole chest wall exceeds 115% (or 120% if electrons are used).
 - Greater than 1 cc of the heart receives a fraction dose exceeding 2 Gy.
 - Dose delivered over a period of time extending greater than the limits defined above.
 - Brachial plexus dose in excess of 107% of the prescription dose.
 - [REDACTED]

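### The stated 15-19 day treatment time omits permitted boosted courses of 20 or 21 days, and 16.6 ties removal from study to a time frame it does not name

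*Combined protocol and SAP*

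**What the plan says.** Section 7.5 gives 11 chest wall fractions and, at the physician's discretion, a scar boost of up to 4 more, so 11 to 15 in all. On timing it says: "Treatment may be started on any weekday, and will not be given over holidays or weekends". Section 7.6 sets one fraction per day and then states "Total Elapsed Time is 15-19 days". Section 17.4 pairs 11-15 fractions with 15-19 days.

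The NOTE in 7.6 deals with interruptions: "Typically 1-2 missed days are simply added to the end of the treatment course for the same total dose". Beyond 2 skipped days, or more than 3 consecutive days without treatment, the investigators discuss the case, and the "decision to retain patient on treatment or remove patient from study will be made by consensus decision of" a group whose name is redacted.

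Two later sections depend on a time limit without naming it:

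- Section 7.9 lists as unacceptable: "Dose delivered over a period of time extending greater than the limits defined above".
- Section 16.6 defines compliance as finishing radiotherapy within a time frame described earlier, and says a patient who cannot do so will be removed from the study.

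Section 8 makes everyone who received one dose evaluable for toxicity.

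**The concern.** A range of 15-19 days for 11-15 weekday fractions looks right if every course starts on a Monday, but 7.5 does not require that. A later start can put one more weekend inside a longer course.

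On its own this would be a slip in a descriptive figure. It gains weight because 16.6, in the statistical section, attaches removal to a time frame found somewhere earlier, and 7.6 is the natural place to look. Section 7.6 holds two different things: a day range and a missed-day rule. If 16.6 means the day range, patients treated exactly as 7.5 permits could be classed as non-compliant and removed. If it means the missed-day rule, they would not be.

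What is at stake is mainly the locoregional recurrence estimate, which 16.2 plans on a fixed 67 patients. Section 8 secures the toxicity denominator; no visible text does the same for recurrence. The boost is a physician's choice, so removals concentrated among boosted patients could make the analysed group unrepresentative of those treated.

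**Working it through.** **Inputs.** Number of fractions n = 11 to 15 (7.5); one fraction per day (7.6); any weekday start and no weekend treatment (7.5); 0, 1 or 2 missed weekdays m added at the end (7.6 NOTE). No holidays are assumed.

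**Formula.** Count calendar days inclusively from first to last fraction. Let s = 0 for a Monday start through 4 for a Friday start. The course spans n + m weekdays, and each weekend crossed adds two days:

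E = (n + m) + 2 × floor[(n + m − 1 + s) / 5]

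**The plan's own figure.** For a Monday start with m = 0:

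- n = 11: 11 + 2 × floor(10/5) = 15 days.
- n = 15: 15 + 2 × floor(14/5) = 15 + 4 = 19 days.

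So 15-19 is exactly the Monday-start range.

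**All permitted starts, no missed day.**

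| Fractions | Mon | Tue | Wed | Thu | Fri |
|---|---|---|---|---|---|
| 11 | 15 | 15 | 15 | 15 | 15 |
| 12 | 16 | 16 | 16 | 16 | 18 |
| 13 | 17 | 17 | 17 | 19 | 19 |
| 14 | 18 | 18 | 20 | 20 | 20 |
| 15 | 19 | 21 | 21 | 21 | 21 |

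For example, 15 fractions from a Tuesday: 15 + 2 × floor(15/5) = 21. Fourteen from a Wednesday: 14 + 2 × floor(15/5) = 20.

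The full range is 15-21 days. Combinations above 19 days: 3 at 14 fractions plus 4 at 15 fractions = 7 of 25, leaving 18 within the range. All 7 include a boost. A full-boost course fits only from a Monday.

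**Other counting convention.** Last date minus first date takes one day off each entry and gives 14-20, which does not match 15-19 either.

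**With the make-up days that the NOTE allows.**

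- 11 fractions: 16-18 days with one, 17-19 with two. Never above 19.
- 13 fractions with one, or 12 with two: 18 days from Monday or Tuesday, 20 from Wednesday to Friday.
- 15 fractions: 22 days from any start with one; 23 with two, or 25 from a Friday.

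So with up to two weekdays lost, only boosted courses can exceed 19 days. A holiday acts like a missed weekday.

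**Consequence under each reading of 16.6**, for uninterrupted courses:

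| Time frame meant | Permitted course types failing |
|---|---|
| 19 days in 7.6 | 7 of 25, all boosted |
| Missed-day rule in the 7.6 NOTE | 0 of 25 |

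These are course types, not patients. The boost rate and the distribution of start days are not given, so they cannot be turned into a number of women.

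**The case against.** The best defence is that 15-19 days is a nominal Monday-start figure. Section 2.4 uses a similar convention: its 39 days for 30 fractions is a Monday-start date difference (30 + 2 × 5 − 1 = 39). Section 17.4 is a convenience comparison, and 7.6 never calls its range a limit. This explains where the figure came from. It does not make the range correct for the starts that 7.5 expressly allows, and neither 7.6 nor 17.4 says it is nominal.

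Next, the NOTE is arguably the better referent for 16.6, since it is the only visible text with a tolerance for missed days and a retain-or-remove decision. A cross-reference need not repeat the rule it points to. This stands as a plausible reading, and it is why the removal problem is conditional.

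Third, removal may mean only that protocol treatment stops. Section 10 frames it that way, 4.1 says patients are followed regularly after treatment, and 16.2 plans recurrence on a fixed 67. No visible text excludes late finishers from the recurrence analysis. That also stands, but no visible text expressly keeps them either.

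Last, the end of the 7.6 NOTE, part of 7.10.1 and the final unacceptable item in 7.9 are redacted, and each could settle the matter. Visible 7.9 itself only applies a plan-quality label.

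A reader might also infer a 15-day limit from the opening of Section 7 ("over 11 weekdays (for 15 elapsed days") or from the schema in 4.2.1 ("15 elapsed days (mastectomy scar boost optional up to 4 fractions"). The documents do not support this. Both tie 15 days to the 11-fraction course and mention the boost as a separate option. The 7.9 item "Dose delivered once a day for 11 daily treatments for PMRT on consecutive weekdays" is likewise written for 11 treatments. None of these is a limit for boosted courses.

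**Conclusion.** The day range in 7.6 and 17.4 is wrong as written. Uninterrupted permitted courses take 15-21 days, and 7 of 25 fraction/start-day combinations, all boosted, exceed 19. This rests only on visible text, inclusive counting and the absence of holidays.

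The time frame meant in 7.9 and 16.6 is unclear rather than wrong. Removal of on-schedule boosted patients follows only if 16.6 means the 19 days. In that case, with no more than two weekdays lost, removals would fall on boosted patients alone.

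Two stronger conclusions are tempting and not supported. One is that removals would cut the power of the primary toxicity test: Section 8 keeps anyone who received one dose evaluable for toxicity. The other is that the recurrence estimate is shown to be biased: the number affected is unknown, the referent is open, and redacted text may bear on practice. Severity is minor.

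**What to change.** 1. In 7.6 and 17.4, give the elapsed time as 15-21 days depending on the number of fractions and the start day, plus holidays and the make-up days that the NOTE allows.
2. In 7.9 and 16.6, cite the missed-day rule in 7.6 by section number in place of the open reference to earlier text.
3. In 16.6, state that a patient who misses the time frame may stop protocol treatment under 7.6, 7.10 or Section 10, but that everyone who received at least one dose stays in follow-up and in both the toxicity and the locoregional recurrence analyses, with schedule compliance reported separately. This extends the Section 8 principle to recurrence and leaves the existing rules for stopping treatment in place.

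The cost is wording in the protocol and its statistical section. No patients, visits or procedures are added.

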7.7 Homogeneity and Reference Points

- ◊ The dose within the PTV for chest wall RT must be within 90-115% of the prescribed dose for the chest wall. Wedges, field in field, and electronic compensation can be used to achieve this endpoint, although a medial wedge greater than 15 degrees is not allowed. A contour for PTV on the chest wall is not required. The treating physician should judge coverage of treatment volume by the 90 percent isodose line on each slice of the axial treatment plan. The point-dose hotspot in this volume should not exceed 115%.
- ◊ The change in dose from minimum to maximum within the treatment volume will be <25% for the external beam plan.

- ◊ If electrons are used on the chest wall, maximum doses of 120% are allowed but should not exceed 2cc of volume.

7.8 Treatment Technique

- ◊ Treatment planning may be performed at any time after consent and registration.
- ◊ Treatment must be performed using CT-Guided planning with the capability of performing true 3-dimensional reconstruction.

7.8.1 Use of a matched 3rd field to treat the supraclavicular lymph nodes at the discretion of the treating radiation oncologist is allowed. It is anticipated that the majority of women receiving postmastectomy RT will have matched fields for regional lymphatic irradiation. Dose will be prescribed to a depth of 3 cm, or to the deepest point of a contour representing the supraclavicular lymph nodes, using a single AP field as is done routinely.

7.8.2 Use of a matched 4th field as a posterior axillary boost (PAB) to treat the axilla at mid-depth is allowed at the discretion of the treating radiation oncologist. As is routinely done, a single PA field will be used to supplement the dose contribution from the AP supraclavicular field to the midplane at the level of the axilla to bring it to the prescription dose.

7.8.3 Wedges are allowed although a medial wedge greater than 15 degrees is not allowed.

7.8.4 Use of bolus is allowed on the chest wall fields at the discretion of the treating physician.

7.8.5 A block should be drawn on the BEVs for all chest wall fields when necessary to completely exclude the heart from the primary beam if this can be achieved without compromising target coverage.

7.8.6 The position of the brachial plexus will be contoured using the brachial/axillary vessels as a surrogate anatomical landmark. Dose to this volume should be constrained to 100% of the prescription dose; however a maximum dose of 107% is considered an acceptable.

7.9 Quality Assurance of Dose Distribution

Each treatment plan shall be judged as:

- **Acceptable:**
 - Dose volume histogram analysis of the target volume confirms 90% of the prescribed dose covers $\geq 90\%$ of the PTV.
 - Dose delivered once a day for 11 daily treatments for PMRT on consecutive weekdays.
 - No greater than 3 cm of lung should be visible at any level of the tangent beam on beam's eye view.

- Heart excluded from primary beam on chest wall fields. If the heart is included in the field, no greater than 1cc of a heart is allowed to receive a fraction dose exceeding 2 Gy.
- Minimum and maximum doses within 90-115% of prescription dose.
- Electron plans (typically for the scar boost) allow 120% of prescription dose as maximum dose provided the volume receiving 120% does not exceed 2 cc.
- **Unacceptable:**
 - Dose volume histogram analysis of the target volume shows < 90% of the prescribed dose covers < 100% of the PTV.
 - Maximum dose on the whole chest wall exceeds 115% (or 120% if electrons are used).
 - Greater than 1 cc of the heart receives a fraction dose exceeding 2 Gy.
 - Dose delivered over a period of time extending greater than the limits defined above.
 - Brachial plexus dose in excess of 107% of the prescription dose.
 - [REDACTED]

7.10 Dose Adjustments/Delays/Modifications/Removal from study

- 7.10.1 **Treatment Breaks/Interruptions:** Radiotherapy is given in continuous course. It is not anticipated that treatment breaks should be needed. If a break seems necessary or must be given due to unavoidable medical necessity (i.e., intercurrent illness), [REDACTED]
- 7.10.2 **Removal From Study:** [name] should be notified within 48 hours by telephone or e-mail and within 7 working days by writing of the removal of a patient from protocol.
- 7.10.3 **Inability to Adequately Perform Treatment Planning:** If the radiation oncologist is unable to devise a dosimetrically-satisfactory treatment plan, then the patient will be removed from study.
- 7.10.4 **Recurrence During Treatment:** Any evidence of local, regional or distant recurrence during the period of therapy will result in removal from study. Further, local-regional and systemic therapy will be at the discretion of the attending physicians. Patients who develop recurrence subsequent to the completion of the treatment program will be managed as deemed appropriate by the attending physicians.
- 7.10.5 **Undue Toxicity:** Treatment may terminate prior to its planned completion should the attending physicians feel that the patient is suffering undue toxicity. Such situations should be discussed with [REDACTED] from study.

7.10.6 **Patient Refusal to Continue Treatment:** A patient may withdraw her consent to participate at any time. In this case, alternative therapy, or no further therapy, may be given at the discretion of the attending physician.

7.11 Anticipated Toxicity

Erythema and desquamation in the vicinity of the treated volume are anticipated to occur. Some patients may develop a moist desquamation, which usually heals within a few weeks. Cellulitis is rare, however. Fatigue is also to be expected. Toxicities will be recorded using CTCAE v 4.0 and attribution of AEs will be recorded.

7.11.1 **Toxicity Management:** Appropriate medical & skin care should be given according to standard practices per departmental guidelines.

7.12 Concomitant Medications

Patients are allowed to continue all prescription medications as they had previously been prescribed. Patients are discouraged to use herbal remedies during the course of radiation therapy, as their interaction with radiation are not very well understood. For patients receiving chemotherapy, chemotherapy may start either before or after radiation treatments, however, there must be a minimum of 3 weeks between chemotherapy and radiation treatments.

7.13 Supportive Care Guidelines

Patients are allowed to receive full supportive care therapies concomitantly during the study such as anti-emetics, skin care, and antibiotics. No other chemotherapy, immunotherapy, or experimental medications will be permitted while the patients are receiving radiation therapy. The use of hormonal cancer therapy during radiation therapy is allowed. Patients may be enrolled on other clinical trials if they do not conflict with the use of radiation therapy as described above.

8. Toxicity Monitoring and Adverse Event Reporting

All patients who receive one dose of protocol therapy will be evaluable for assessment of toxicity. Prior to each cycle the treating physician or their designee will fully assess the patient's condition with respect to possible treatment related toxicities. All adverse events Grade 2 or greater related to radiation therapy, whether observed by the physician or reported by the patient, occurring during the active portion of therapy, or up to 30 days after the last dose of treatment will be graded by a numerical score according to the National Cancer Institutes' (NCIs') Common Terminology Criteria for Adverse Events (CTCAE), Version 4.0 (<http://ctep.cancer.gov/reporting/ctc.html>) and recorded in the patient's medical record. Toxicities (including laboratory abnormalities) will be reported as outlined in the data capture plan.

A preexisting condition is one that is present at the start of the study. A preexisting condition will be recorded as an adverse event if the frequency, intensity, or the character of the condition worsens during the study period.

The Investigator will follow all patients who experienced an AE until there is a return to the patient's baseline condition or until a clinically satisfactory resolution is achieved.

8.1 Adverse Events.

8.1.1 Reporting Requirements

- ◊ An adverse experience is defined as any unintended or abnormal clinical observation that is not of benefit to the patient. Either the condition was not present prior to exposure to the study therapy, or it has worsened in intensity or frequency following exposure to the study therapy.
- ◊ All "unexpected" (defined below) and/or "serious" (defined below) adverse events occurring during the active portion of therapy or up to 30 days after the

8.2 Definition of Serious Adverse Events (SAEs)

A serious adverse event (experience) is one occurring at any dose level that results in any of the following outcomes:

- Death
- Life-threatening- immediate risk of death from the reaction.
- Requires inpatient hospitalization or prolongation of existing hospitalization.
- Results in persistent or significant disability/incapacity.
- Results in a congenital anomaly/birth defect.
- Requires intervention to prevent one of the outcomes listed in this definition.

The definition of serious adverse event (experience) also includes important medical events. Medical and scientific judgment will be exercised in deciding whether expedited reporting is appropriate in other situations, such as important medical events that may not be immediately life-threatening or result in death or hospitalization but may jeopardize the patient or may require intervention to prevent one of the other outcomes listed in the definition above. These events will usually be considered serious.

8.3 Definition of Related Adverse Events

8.3.1 There is a reasonable possibility that the drug caused the adverse experience. That is, the event is judged by the investigator to be possibly, probably or definitely related to the treatment.

8.4 Definition of Unexpected Adverse Events

8.4.1 Any adverse drug experience and/or specificity, that is not included in the current investigator's brochure and/or package insert.

9. Treatment Evaluation/Criteria for Response

- ◊ Loco-regional (LR) control will be assessed by physical examination and other relevant imaging per the discretion of the patients treating physicians. All LR failures have to be confirmed by biopsy, and should be coded as either chest wall recurrence, axilla, supraclavicular, or internal mammary.

9.1 Toxicity

9.1.1 The Common Terminology Criteria for Adverse Events version 4.0 (CTCAE) (<http://ctep.cancer.gov/forms/CTCAEv4.pdf>) for acute toxicity of the skin will be used to score and report acute toxicity.

- ◊ Patients will be seen in follow-up weekly during treatment, at the end of radiation, then 2-8 weeks after RT, 3-6 months for 3 years, then every 6-12 months out to 5 years.

9.1.2 Additional toxicity end points:

[figure not shown]
- ◊ **Brachial plexopathy:** Investigators should record information relevant to brachial plexopathy at each follow-up visit, and include 1) method of detection, 2) signs & symptoms, and 3) method of treatment (see CRF in Appendix D).
- ◊ **Pain:** Information about pain should be recorded at each visit as documented in the CRF in Appendix D.
- ◊ **Pigmentation and Telangiectasia:** Information regarding skin pigmentation and telangiectasia will be recorded at each follow-up visit and graded I-IV (refer to CRF in Appendix D).

